5.1 Study treatment

5.1.1 Investigational and control drugs

During the core study patients in both treatment arms, A and B, receive the same study drug supplied by Novartis and appropriately labeled:

Secukinumab 300 mg, provided as two s.c. injections of 1 ml prefilled syringe (PFS). Each 1 ml syringe contains 150 mg Secukinumab.

5.1.2 Additional treatment

Patients in arm B receive additional treatment in form of a lifestyle intervention.

The lifestyle intervention is based on a structured and standardized program, closely guiding patients with metabolic syndrome with the primary goal to improve their metabolic status and to lose weight. The program and its content is designed by the [REDACTED] under the

leadership of [name]. med. [REDACTED] especially for this trial. It is tailored to the needs of the trial's patient population and optimized for combination with Secukinumab therapy. Patients are individually and regularly supervised by qualified trainers. They receive standardized education in nutrition, physical activity and metabolism, they learn about effects of nutrition and physical activity and they are consulted how to change their habits, their diet and how to increase their physical activity level. The lifestyle intervention actively enforces patient's own motivation for lifestyle changes, with the goal to induce long-lasting changes in nutritional and physical activity habits leading to sustained weight reduction and improvement of metabolic status. Patients receive tracking devices, which support patient's own motivation. The program is conducted in a standardized way, meaning that educational material and teaching is standardized and trainers, who perform the lifestyle intervention, have received standardized instructions (workshop and written information) before they can instruct patients. All trainers have to participate in a workshop conducted by [REDACTED] to qualify for counseling of the patients. The trainers are also instructed to report (serious) adverse events that are mentioned by the patient during the lifestyle intervention program or that occur during the training within 24 hours to the respective investigator. The investigator will assess whether the event constitutes a non-serious or serious adverse event and report it, if applicable. The main principle of the lifestyle intervention program is based on the programs applied in two milestone trials in the field of lifestyle intervention in patients with metabolic syndrome (Knowler et al., 2002; Tuomilehto et al., 2001). Details of the lifestyle intervention program are given in a separate manual.

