ability to lose weight under these medications (weight gain is a well-known side effect of insulin and sulfonylurea agents/analogues). Patients with type 2 diabetes receiving other medications, such as DPP4 inhibitors, are allowed to participate in the study, as lifestyle intervention is the guideline-recommended basic therapy for any patient with type 2 diabetes (NVL Therapie des Type-2-Diabetes), and offers benefit for them, which outweighs the potential small risk of hypoglycemia or ketoacidosis in the case of metformin. The treating family physicians of the patients participating in the lifestyle intervention will be notified about the participation in the lifestyle intervention, so they can adequately monitor them and adjust their antidiabetic or antihypertensive medication.

Based on the current knowledge no interactions with negative consequences between Secukinumab therapy and lifestyle intervention can be expected. On the contrary, it is the goal of this study to assess potential positive effects of the combined application. The risk will be further minimized by close clinical and laboratory monitoring of participating patients at all study visit.

The additional risks of participating in the biomarker sub-study are those of blood sampling. Blood sampling will occur at time points where standard blood sampling is scheduled as well, and will not require additional venipuncture. Participation in the sub-study does not negatively affect the overall risk-benefit ratio for participation in the study.

4 Population

The study is conducted in Germany and the study population consists of a representative group of male and female patients (≥ 18 years old) with moderate to severe plaque-type psoriasis and concomitant metabolic syndrome according to International Diabetes Federation (IDF), American Heart Association (AHA), and National Heart, Lung and Blood Institute (NHLBI) consensus definition from 2009 (Alberti et al., 2009). The goal is to randomize a total of approximately 760 patients in approximately 100 sites in Germany. Considering analyses of prior studies and the inclusion criterion metabolic syndrome, a screening failure of 30 % is expected, making screening of approximately 1100 patients necessary in order to provide the required number of patients.

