5.2 Treatment arms

Core study: The study has two different treatment arms:

- **Arm A:** Patients in arm A receive therapy with Secukinumab 300 mg s.c., which consists of two injections with 150 mg prefilled syringes at weeks 0, 1, 2, 3, 4, 8, 12, 16, 20 and 24 (last injection is performed at week 24)
- **Arm B:** Patients in arm B receive therapy with Secukinumab 300 mg s.c., which consists of two injections with 150 mg prefilled syringes at weeks 0, 1, 2, 3, 4, 8, 12, 16, 20 and 24 (last injection is performed at week 24). **In addition they participate in a lifestyle intervention program.**

Extension period: After 28 weeks the study continues with an extension period, during which lifestyle intervention is offered to all patients, irrespective of their prior treatment arm. This means that patients of arm B, who are willing to, can continue their previously started lifestyle intervention program and patients of arm A, who are willing to, can start the lifestyle intervention program at the beginning of the extension period. The extension period ends at week 56. There will be no study drug supply during the extension period. The treating physician is free to choose suitable psoriasis therapy for each patient.

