7.1 Adverse events

An adverse event (AE) is any untoward medical occurrence (e.g., any unfavorable and unintended sign [including abnormal laboratory findings], symptom or disease) in a subject or clinical investigation subject *after providing written informed consent* for participation in the study until the end of study visit. Therefore, an AE may or may not be temporally or causally associated with the use of a medicinal (investigational) product. Medical conditions/ diseases

present before first intake of study drug are only considered adverse events if they worsen after study start.

In addition, all reports of intentional misuse and abuse of the product are also considered an adverse event irrespective if a clinical event has occurred.

The occurrence of adverse events must be sought by non-directive questioning of the patient at each visit during the study. Adverse events also may be detected when they are volunteered by the patient during or between visits or through physical examination findings, laboratory test findings, or other assessments.

Abnormal laboratory values or test results constitute adverse events only if they fulfill at least one of the following criteria:

- they induce clinical signs or symptoms,
- they are considered clinically significant,
- they require therapy.

Clinically significant abnormal laboratory values or test results must be identified through a review of values outside of normal ranges/clinically notable ranges, significant changes from baseline or the previous visit, or values which are considered to be non-typical in patient with underlying disease. Investigators have the responsibility for managing the safety of individual patient and identifying adverse events. Alert ranges for laboratory and other test abnormalities are included in Appendix 1. Clinically significant abnormal laboratory values will also be assessed for the following parameters of the biomarker sub-study (only for patients participating in the biomarker sub-study): Adiponectin, leptin, insulin, HOMA-IR, proinsulin, IL-6, TNF-alpha, M30 assay, NT-proBNP.

Adverse events must be recorded in the Adverse Events CRF under the signs, symptoms or diagnosis associated with them, accompanied by the following information:

- the severity grade
 - mild: usually transient in nature and generally not interfering with normal activities
 - moderate: sufficiently discomforting to interfere with normal activities
 - severe: prevents normal activities

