2.4.2.2 Lifestyle intervention

Compliance as percentage of lifestyle intervention visits participated in will be calculated as the number of intervention visits attended (based on documented participation counts as given in the lifestyle intervention record eCRF page) divided by the number of lifestyle intervention visits scheduled per protocol until discontinuation. It is to be noted that for dropouts/discontinuations, the denominator will be adjusted to number of intervention visits participated scheduled per protocol until discontinuation.

It is given by the formula:

Compliance (%) = $100 * (\text{total no of lifestyle intervention visits participated}) / (\text{no. of lifestyle intervention visits scheduled})$

In the core study selection phase lifestyle intervention visit are scheduled at weeks 0, 1, 2, 3, 4, 8, 16 and 24. In the extension study phase the visits are scheduled for weeks 36, 44 and 56. Patients in Arm A starting lifestyle intervention during the extension phase will have their first

lifestyle intervention at week 28. Patients in Arm A do not have a lifestyle intervention at week 56. Patients in Arm B have lifestyle intervention visits at E1, E2 and E3.

Compliance percentage will be summarized for the SAF dataset (displaying totals) by treatment group and also by categories (< 80% and ≥ 80% to 100%).

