2.9.1 Adverse events

Treatment emergent adverse events (events started after the first dose of secukinumab study treatment or events present prior to the first dose of secukinumab study treatment but increased in severity) will be summarized by preferred term up to 28 weeks after the first dose..

AEs will be summarized by presenting, for each treatment group, the number and percentage of patients having any AE, having an AE in each primary system organ class (SOC) and having each individual AE (preferred term).

Summaries will also be presented for AEs by severity and for secukinumab study treatment (with and without life-style intervention) related AEs. If a patient reported more than one adverse event with the same preferred term, the adverse event with the greatest severity will be presented. If a patient reported more than one adverse event within the same primary SOC, the patient will be counted only once with the greatest severity at the SOC level, where applicable. Furthermore, a listing of all adverse events, including SAE, will be provided. SAEs will be summarized.

Separate summaries will be provided for death, SAE, other significant AEs leading to secukinumab study treatment (with and without life-style intervention) discontinuation and AEs leading to dose adjustment (including secukinumab study treatment discontinuation).

Deaths occurring after signing of informed consent and prior to the start of the core study will be presented in the listing.

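### In the core study only arm B has trainers who forward adverse events, and nothing listed in the plan records that route, so by-arm AE percentages may be biased upward in arm B by an unknown amount, possibly zero

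*Protocol*

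**What the plan says.** **Shared ascertainment.** Protocol 7.1 applies to both arms: "The occurrence of adverse events must be sought by non-directive questioning of the patient at each visit during the study". Events that patients volunteer at or between visits also count in both arms. Table 6-1 marks (S)AE assessment at every visit.

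**Arm B's extra channel.** Protocol 5.1.2 assigns the programme to one arm: "Patients in arm B receive additional treatment in form of a lifestyle intervention". It then says: "The trainers are also instructed to report (serious) adverse events that are mentioned by the patient during the lifestyle intervention program". The same sentence covers events that occur during training and sets a 24-hour limit for passing them to the investigator. The next step is: "The investigator will assess whether the event constitutes a non-serious or serious adverse event and report it, if applicable". Core SAP 2.4.2.2 gives the core-study schedule: "lifestyle intervention visit are scheduled at weeks 0, 1, 2, 3, 4, 8, 16 and 24".

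**What is recorded.** Protocol 7.1 lists severity, relationship (to study treatment, lifestyle intervention, both or neither), duration, seriousness, action taken and outcome. Route or source of the report is not on the list.

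**What is tabulated.** Core SAP 2.9.1: "AEs will be summarized by presenting, for each treatment group, the number and percentage of patients having any AE". The window for treatment-emergent events is 28 weeks from first dose. Summaries by severity and by relatedness are planned. No AE test, interval or model is specified in that section, and there is no summary by source.

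**Bias discussion.** Protocol 3.2 considers open-label bias for PASI and for laboratory and technical measures. It does not mention AEs.

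**Extension.** The asymmetry is not built in after week 28: "patients of arm A, who are willing to, can start the lifestyle intervention program at the beginning of the extension period".

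**The concern.** Both arms receive the same drug on the same schedule, so the by-arm AE contrast is the trial's evidence on the safety of adding the lifestyle programme, and the study title names safety as part of the comparison. For the whole window of the core AE table, arm B has a second listener with an instruction to report, and arm A does not. Mild events are the ones most likely to be mentioned in a counselling session and left out of a non-directive exchange at the clinic.

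If arm B shows more AEs, there are two explanations: the programme causes events, or the trainers bring to light events that arm A also has but does not report. The relationship field does not separate them. It records the judged cause of an event, not how the event came to be known. On the items listed, nobody could later check which explanation applies.

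**Working it through.** The plan gives no AE rate and no detection figure, so it has no figure of its own to reproduce here. The sample-size figures are not used.

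**Step 1: scheduled contacts, weeks 0 to 28.**
- Site visits with AE assessment (Table 6-1, visits 2 to 12): weeks 0, 1, 2, 3, 4, 8, 12, 16, 20, 24, 28 = 11, both arms.
- Trainer visits (core SAP 2.4.2.2; same pattern in Table 6-1): weeks 0, 1, 2, 3, 4, 8, 16, 24 = 8, arm B only.
- Arm A 11; arm B 11 + 8 = 19; ratio 19/11 = 1.73.
- Trainer weeks without a site visit: 0 of 8.

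The channel adds conversations, but no new scheduled week.

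**Step 2: range of the possible excess.** Assume the same true AE risk R in both arms. Let s be the share captured through the site, and f the share of missed events that trainers recover.
- Arm A = R × s
- Arm B = R × (s + (1 − s) × f)
- Excess = R × (1 − s) × f

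None of these inputs is in the documents. Assumed ranges: R 10% to 60%, s 0.80 to 1.00, f 0 to 0.5.
- Lowest: s = 1 or f = 0 gives 0 points.
- Middle example: R = 0.6, s = 0.9, f = 0.25 gives 54.0% against 55.5%, or +1.5 points (ratio 1.03).
- Highest: 0.6 × 0.2 × 0.5 = 0.060, or +6.0 points (48.0% against 54.0%, ratio 1.125).

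**Step 3: what excluding trainer-first events would do.** Assume Poisson event counts, 60% of arm A with any AE, no true difference, and no trainer-first event occurring during training. Then m = −ln(0.40), and a multiplier c on the event count gives a percentage with any AE of 1 − 0.4^c.

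| Arm B scenario | All-source | Excluding trainer-first | B − A: exclusion table to all-source table |
|---|---|---|---|
| 20% extra events, known only through trainers | 1 − 0.4^1.2 = 66.7% | 1 − 0.4^1.0 = 60.0% | 0 to +6.7 |
| No extra events; 20% merely told to the trainer first | 1 − 0.4^1.0 = 60.0% | 1 − 0.4^0.8 = 52.0% | −8.0 to 0 |
| 10% extra and 10% told to the trainer first | 1 − 0.4^1.1 = 63.5% | 1 − 0.4^0.9 = 56.2% | −3.8 to +3.5 |

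The true difference, 0, lies inside or at the edge of every range. Neither table alone can be relied on. The all-source table can over-count arm B. The exclusion table can under-count it, because an event told first to the trainer may be one that the site visit would have picked up anyway. These rows show how the two tables behave; they do not estimate what happened in the trial.

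**The case against.** The case for leaving the plan alone has real force.

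- **The extra channel may add nothing.** Every trainer visit falls in a week with a site visit, and volunteered events count in both arms. Trainers are told to pass on what they hear, with no stated duty to ask. The investigator screens each report. This stands, and it is why zero is inside the range. It does not close the question: the recommended windows (protocol section 6: ±2 days for visits 2 to 6, ±5 days for visits 7 to 12) do not require the same day, the listener is different, and the investigator can screen only what arrives.
- **The AE tables are descriptive.** This stands. A reader might want to quote the chance of a nominally significant excess, but that would describe a test which SAP 2.9.1 does not plan.
- **Some trainer-reported events are real harm.** This stands, above all for events during training. A reader might infer that the main comparison should use only routes common to both arms. That would remove such harm and could produce a false benefit for arm B, as the second scenario in the table shows (52.0% against 60.0%).
- **Relatedness is already collected.** This helps to separate intervention-related events from others, but it does not show how an event was found.
- **Key documents are not available.** The AE eCRF and the lifestyle manual were not seen, so the missing source field is inferred from the list in protocol 7.1.
- **No safety objective is visible** among the primary and secondary objectives. This lowers the weight of the point without removing it, since AE tables by arm are planned.

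A reader might also count family physicians as a further channel, because protocol 3.6 says: "The treating family physicians of the patients participating in the lifestyle intervention will be notified about the participation". The stated purpose is monitoring and adjusting antidiabetic or antihypertensive medication. They are given no duty to report AEs to the site, so the documents do not support that reading.

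**Conclusion.** The point holds as a possible upward bias in arm B's core-study AE percentages, of a size the documents do not allow to be estimated. The illustrative range is 0 to 6.0 percentage points; its upper end reflects the chosen inputs and nothing in the plan. What is firm is structural: one arm has an additional reporting channel throughout the tabulated period, and neither the listed AE items nor the planned tables can show what it contributed.

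A reader might infer that arm B's harm is inflated by detection. The documents do not support that as a fact, because capture at site visits could already be complete. Nor does the asymmetry extend by design beyond week 28, when arm A patients may take up the programme.

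The conclusion assumes that the AE eCRF holds no source field beyond the items in protocol 7.1, and that trainer contacts are the 8 in the SAP. If the separate manual schedules more, the imbalance in contacts would be larger.

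**What to change.** 1. Add one field to the AE eCRF: route of first report (site visit / spontaneous to site / lifestyle trainer / other).
2. In core SAP 2.9.1, keep the all-source by-arm table as the primary AE summary.
3. Add a sensitivity table that excludes events first reported through a trainer, but retains those that occurred during training.
4. List trainer-route events separately.
5. State in the SAP that the two tables bracket the detection effect: the all-source table is the upper end, and the sensitivity table is the lower end because it can drop arm B events that the site would have heard anyway.

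SAE reporting is unchanged, and nothing in patient care is affected. The cost is slightly more data entry and one extra table set.

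The extension SAP's document history has an entry dated after final database lock. If data collection has closed, the fallback is to retrieve the route from source notes where it was written down, and to state the difference in ascertainment as a limitation in the study report.

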5.2 Treatment arms

Core study: The study has two different treatment arms:

- **Arm A:** Patients in arm A receive therapy with Secukinumab 300 mg s.c., which consists of two injections with 150 mg prefilled syringes at weeks 0, 1, 2, 3, 4, 8, 12, 16, 20 and 24 (last injection is performed at week 24)
- **Arm B:** Patients in arm B receive therapy with Secukinumab 300 mg s.c., which consists of two injections with 150 mg prefilled syringes at weeks 0, 1, 2, 3, 4, 8, 12, 16, 20 and 24 (last injection is performed at week 24). **In addition they participate in a lifestyle intervention program.**

Extension period: After 28 weeks the study continues with an extension period, during which lifestyle intervention is offered to all patients, irrespective of their prior treatment arm. This means that patients of arm B, who are willing to, can continue their previously started lifestyle intervention program and patients of arm A, who are willing to, can start the lifestyle intervention program at the beginning of the extension period. The extension period ends at week 56. There will be no study drug supply during the extension period. The treating physician is free to choose suitable psoriasis therapy for each patient.

5.3 Treatment assignment and randomization

Patients will be randomized in a 1:1 ratio to one of the two treatment arms at randomization visit. Randomization will be performed by the use of sealed envelopes. The investigator or his/her delegate will open the sealed envelope after confirming that the patient fulfills all ex- and inclusion criteria. The envelope will assign a randomization number to the patient, which can be used to link the patient to a treatment arm.

The randomization numbers will be generated using the following procedure to ensure that treatment assignment is unbiased and concealed from patients and investigator staff. A patient randomization list will be produced by the provider using a validated system that automates the random assignment of patient numbers to randomization numbers. These randomization numbers are linked to the different treatment arms.

The randomization scheme for patients will be reviewed and approved by a member of the Randomization Group.

At randomization visit an eligible patient will be given the lowest available randomization number. This number assigns the patient to one of the treatment arms. The investigator will enter the randomization number on the case report form (CRF).

5.4 Treatment blinding

Not applicable, as this study has an open label design.

5.5 Treating the patient

Sponsor qualified medical personnel will be readily available to advise on trial related medical questions or problems.

5.5.1 Patient numbering

Each patient is uniquely identified in the study by a combination of his/her center number and patient number. The center number is assigned by Novartis to the investigative site. Upon signing the informed consent form, the patient is assigned a patient number by the investigator. At each site, the first patient is assigned patient number 1, and subsequent patients/subjects are assigned consecutive numbers (e.g. the second patient is assigned patient number 2, the third patient is assigned patient number 3). Once assigned to a patient, a patient number will not be reused. If the patient fails to be randomized for any reason, the reason for not being randomized will be entered on the Screening Log. Additional information to be collected on Screening Failures is described in Section 6.1.

